4. PARTICIPANT ENTRY

4.1. PRE-REGISTRATION EVALUATIONS

GP/ nurse practitioner obtains certain data before refereeing patient for DVT Scan: age, gender, underlying malignancy, pregnancy, previous DVT (if yes: when, where). This information gets obtained when estimating the Wells Score as one of the main indicators for DVT. Furthermore, the referring GP would take a blood test to test for elevated D-Dimer, as second indicator for DVT. If the blood test was not obtained from the GP or the result is unknown, it will get retested at the DVT clinic.

4.2. INCLUSION CRITERIA

Patients are eligible for this trial if:

1. The participant has capacity to consent, and consent is obtained
2. The participant is an adult (18 or older in the UK)
3. The participant has symptoms suggestive of a deep venous thrombosis
4. The diagnostic DVT algorithm indicates that an ultrasound is needed

4.3. EXCLUSION CRITERIA

A patient will not be eligible for this study if they fulfil one or more of the following criteria:

1. Patient is under the age of 18 years.
2. No data of D-dimer result
3. The participant is found to have a distal DVT during the US scan (retrospective exclusion)
4. Participant did not sign consent form

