AIMS "AutoDVT" is a software system designed to assist non-specialist operators, such as nurses, general practitioners (GP) and other allied health professionals in the diagnosis of DVT. The software utilises a "machine learning" algorithm to assist non-specialists in the diagnosis of DVT as described below. Venous thrombosis commonly occurs in the deep leg veins as well as the deep veins of the pelvis, and they are divided clinically into above knee (iliac, femoral, popliteal) and below knee (calf veins) DVT. DVT is well recognised to cause globally significant morbidity and mortality both at the time of diagnosis and post diagnosis. Between 30 – 50% of patients diagnosed with DVT will go on to develop a post-thrombotic syndrome, which has a significant impact on patients' long-term quality of life. Patients with DVT are also at risk of a oft fatal pulmonary embolus (PE), with rates estimated to be 0.4% during the initial anticoagulation period and post-treatment.

According to the Charity Thrombosis UK dies every 37 seconds a person of a venous thromboembolism in developed countries (Thrombosis UK, 2019). However, positive cases only represent 12-25% of the total number of patients who present with suspected DVT. In other words, between 75-88% of suspected DVT cases, when fully investigated, are negative. It is important to note that this does not consider time lost from work, hospitalisation, treatment costs and costs for repeat ultrasound scans. It is notoriously difficult to diagnose a DVT by clinical exam alone. The standard approach to make a diagnosis of proximal DVT currently involves an algorithm combining pre-test probability- Wells Score, D-dimer (blood) testing, and compression ultrasonography (typically a three-point compression examination). There are new handheld ultrasound (US) probes available, meaning only the US probe is required for diagnostic purposes in conjunction with a smartphone or tablet. At present, although the new handheld probes are smaller and are better suited for point of care diagnosis, they still require an experienced radiologist or sonographer to perform the three-point compression exam.

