3. STUDY DESIGN

This is a non-randomised, single-blinded, prospective cohort pilot study.

Participants attending the DVT clinic at St. Mary's NHS Trust with a suspected DVT will be initially screened by the clinical team for potential inclusion into the trial. If the patient is eligible for inclusion, they will be approached to consider taking part in the study. Patients will be given sufficient time to read the participant information sheet, and to consider taking part and ask any questions they may have. If they agree, they will be asked to sign an informed consent form. Once consent has been obtained, [name] will perform the three-point compression ultrasound scan (USS) with the AutoDVT software on the participants. At the end of the scan, the AutoDVT software will indicate "exam complete" or "repeat exam". The AutoDVT software will store the results of the scan for analysis and review. Following the AutoDVT scan, patients will continue with the standard DVT diagnostic pathway, including a standard compression ultrasound scan.

Duration: 5 months

Number and type of subjects: estimation of recruitment of approx. 50 participants

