3.1. STUDY OUTCOME MEASURES

Primary Outcome:

Estimate the sensitivity of the AutoDVT software to detect proximal DVT compared to the gold standard.

Secondary Outcome:

The study will evaluate the accuracy and quality, practicality and user acceptance of the AutoDVT software. (Specificity of AutoDVT, positive and negative predictive values of AutoDVT, imaging failure rates (with reasons), numbers of eligible patients not enrolled (with reasons), duration of AutoDVT scans, number of repeat scans).

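### Removing participants with distal DVT after the scan takes target-negative patients out of specificity and PPV, and the wording leaves open which proximal cases count for sensitivity

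*Protocol*

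**What the plan says.** Section 3.1 sets the primary outcome: "Estimate the sensitivity of the AutoDVT software to detect proximal DVT compared to the gold standard". The secondary outcomes there include "Specificity of AutoDVT, positive and negative predictive values of AutoDVT".

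Entry is by suspicion. Section 4.2 admits consenting adults with suggestive symptoms for whom "The diagnostic DVT algorithm indicates that an ultrasound is needed". Nothing in that list depends on where a thrombus lies.

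Exclusion 3 in Section 4.3, repeated in the Eligibility part of the Study Summary, then removes a participant if "The participant is found to have a distal DVT during the US scan (retrospective exclusion". It does not say whether a proximal DVT may also be present, nor which of the two study scans decides.

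The Aims part of the Study Summary describes DVT as "divided clinically into above knee (iliac, femoral, popliteal) and below knee (calf veins) DVT" and gives no rule for patients with both. It also states that "positive cases only represent 12-25% of the total number of patients who present with suspected DVT". Section 3 gives the size as "estimation of recruitment of approx. 50 participants".

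**The concern.** An accuracy study with a proximal target has two groups: patients with proximal DVT and everyone else. A patient whose only thrombus is in the calf is in the second group. If AutoDVT flags that patient, the flag is a false positive for the stated target; if it does not, the result is a true negative. Removing these patients on a scan finding makes specificity, PPV and NPV describe a group that no AutoDVT user could select beforehand. The intended user in the Study Summary is a community or nursing-home nurse, who would not know distal status before scanning.

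The wording raises a second problem, which reaches the primary outcome. Taken literally, the rule covers a patient with both proximal and distal thrombus. That patient is a proximal case and would leave the sensitivity denominator, which is small to begin with.

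**Working it through.** **Inputs from the protocol.** About 50 participants (Section 3); 12-25% positive among those who present (Study Summary, Aims). This gives 50 × 0.12 = 6 to 50 × 0.25 = 12.5 DVTs of any kind. Prevalence may be higher among those the algorithm sends to ultrasound. The protocol states no PPV or specificity, so there is no figure of its own to reproduce.

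**Direction, isolated distal cases.** Let TP, FN, FP and TN be the counts without the distal patients, D the number of isolated distal cases and f the number of them flagged.

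- PPV as written is TP/(TP+FP); with distal kept, TP/(TP+FP+f). If TP > 0, the first is larger whenever f > 0, and the two are equal when f = 0.
- Specificity as written is TN/(TN+FP); with distal kept, (TN+D−f)/(TN+FP+D). The kept value is a weighted average over the two negative groups. The exclusion therefore overstates specificity if distal patients are flagged more often than patients with no DVT, leaves it unbiased if equally often, and understates it if less often.
- NPV as written is TN/(TN+FN); with distal kept, (TN+D−f)/(TN+D−f+FN). The exclusion never raises it.
- Sensitivity is TP/(TP+FN) in both.

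**Size, all assumed.** Sensitivity is 95% and the false-positive rate in no DVT is 5%. The results are ratios of expected counts. Base mix: 8 proximal, 4 isolated distal, 38 no DVT, so TP = 7.6, FN = 0.4, FP = 1.9 and TN = 36.1. As written: PPV 7.6/9.5 = 80.0%, specificity 95.0%, NPV 36.1/36.5 = 98.9%.

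| Flag rate in distal DVT | Distal flagged | PPV, distal kept | Specificity, distal kept |
|---|---|---|---|
| 0% | 0 | 7.6/9.5 = 80.0% | 1 − 1.9/42 = 95.5% |
| 5% | 0.2 | 7.6/9.7 = 78.4% | 1 − 2.1/42 = 95.0% |
| 15% | 0.6 | 7.6/10.1 = 75.2% | 1 − 2.5/42 = 94.0% |
| 30% | 1.2 | 7.6/10.7 = 71.0% | 1 − 3.1/42 = 92.6% |

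NPV with distal kept is 99.0% in all four rows (40.1/40.5 to 38.9/39.3).

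Other assumed mixes (proximal/isolated distal/none):

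| Mix | PPV as written | Kept, 5% flagged | Kept, 30% flagged |
|---|---|---|---|
| 4/2/44 | 3.8/6.0 = 63.3% | 3.8/6.1 = 62.3% | 3.8/6.6 = 57.6% |
| 16/4/30 | 15.2/16.7 = 91.0% | 15.2/16.9 = 89.9% | 15.2/17.9 = 84.9% |
| 13/7/30 | 12.35/13.85 = 89.2% | 12.35/14.2 = 87.0% | 12.35/15.95 = 77.4% |

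Across the four mixes the PPV shift is about 1 to 2 points at equal rates and about 6 to 12 points at 30%.

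**How often PPV changes at all.** At least one distal patient must be flagged. At 5% the chance is 1 − 0.95⁴ = 18.5% with 4 distal patients and 1 − 0.95² = 9.8% with 2. At 30% it is 1 − 0.7⁴ = 76.0% and 1 − 0.7² = 51.0%.

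**Against sampling error.** A PPV of 8/10 has an exact 95% interval of 44.4% to 97.5%. For specificity with 42 negatives, 1.96 × √(0.926 × 0.074/42) = 7.9 points either side.

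**Literal reading.** With, say, 8 of 9 proximal cases detected (88.9%), dropping two detected cases that also have calf thrombus gives 6/7 = 85.7%; dropping the one missed case gives 8/8 = 100%. This shows only that the denominator is open. It is not an estimate of bias. Under this reading a removed flag can be a true positive, so PPV can fall as well as rise.

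**The case against.** The strongest reply is that little is at stake. Under the probable meaning of the rule the primary outcome is untouched, and the rest concerns secondary outcomes of a pilot. Every rate above is assumed. At equal flag rates in the base mix, no distal patient is flagged in 100 − 18.5 = 81.5% of trials. The larger shifts need distal patients to be flagged six times as often as patients with no DVT, and the protocol gives no reason to expect that from a three-point compression scan. The rule may also rarely apply: Section 1.2 describes the reference as compression at two or three points, which may find few calf thrombi, whereas the Design part of the Study Summary calls it Duplex. And since the software is also described as separating thrombosis from no thrombosis, setting calf thrombosis aside openly and in advance can be defended.

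Most of this stands as a limit on size. It does not rescue the rule. The stated target is proximal DVT, which makes isolated distal cases negatives, not ineligible patients. A larger sample would not remove the selection. Nor can the point simply be left to a SAP: the rule sits in both eligibility lists, so a SAP that kept these patients would contradict the protocol.

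**Conclusion.** The concern holds and should be fixed, as a modest point. The exclusion depends on a scan result and removes target-negative patients from specificity, PPV and NPV. For isolated distal DVT the direction is certain only for PPV, and only if at least one such patient is flagged. The sizes rest entirely on assumed case mixes and flag rates and are likely to lie within sampling error at about 50 participants. No bias in sensitivity is shown. Because the Aims treat above-knee and below-knee DVT as two categories, below-knee only is the probable meaning, but the text does not settle which proximal cases enter a primary denominator that may rest on some 6 to 12 DVTs of any kind.

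**What to change.** Delete exclusion 3 in the Study Summary and in Section 4.3. Keep every participant who has both scans and classify by the reference result in the proximal veins: proximal DVT with or without calf involvement is positive; isolated distal DVT or no DVT is negative. If wanted, report the results without isolated distal DVT as a labelled sensitivity analysis.

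Reconcile the scan order too. The Design part of the Study Summary and Section 1.1 put the specialist scan first; the Population part and Section 3 put AutoDVT first. If the specialist scan came first, patients found to have distal DVT might never receive the AutoDVT scan, and their results could not be recovered.

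The cost is a wording change in two lists of a protocol that already has ethics approval (Section 8.1), plus at most one extra analysis line. Specificity and PPV may come out slightly less favourable. No extra scans are needed if AutoDVT comes first; if the specialist scan does, 2 to 7 more AutoDVT scans in the mixes assumed above.

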4.4. WITHDRAWAL CRITERIA

All patients will be fully informed of the risks/ benefits of the study. They have the right to withdraw.

5. ADVERSE EVENTS

5.1. DEFINITIONS

Adverse Event (AE): any untoward medical occurrence in a patient or clinical study subject.

Serious Adverse Event (SAE): any untoward medical occurrence or effect that:

- Results in death
- Is life-threatening – *refers to an event in which the subject was at risk of death at the time of the event; it does not refer to an event which hypothetically might have caused death if it were more severe*
- Requires hospitalisation, or prolongation of existing inpatients' hospitalisation
- Results in persistent or significant disability or incapacity
- Is a congenital anomaly or birth defect

Medical judgement should be exercised in deciding whether an AE is serious in other situations. Important AEs that are not immediately life-threatening or do not result in death or hospitalisation but may jeopardise the subject or may require intervention to prevent one of the other outcomes listed in the definition above, should also be considered serious.

The potential risks of the intervention are minimal. The participants will require an extra scan of their leg which will increase the diagnostic process time. The participants will be fully informed prior to entry about risks and expected study scan time. Staff doing the extra scan will be thoroughly trained to help minimise participants delay.

5.2. REPORTING PROCEDURES

All adverse events should be reported. Depending on the nature of the event the reporting procedures below should be followed. Any questions concerning adverse event reporting should be directed to the chief investigator or the study coordinator in the first instance.

5.3.1 Non serious AEs

All such events, whether expected or not, should be recorded. It should be specified if only some non-serious AEs will be recorded, any reporting should be consistent with the purpose of the trial end points.

5.3.2 Serious AEs

An SAE form should be completed and emailed to the study coordinator or chief investigator within 24 hours. However, hospitalisations for elective treatment of a pre-existing condition do not need reporting as SAEs.

All SAEs should be reported to the Imperial College Research Ethics Committee (ICREC) where in the opinion of the Chief Investigator, the event was:

- 'related', i.e., resulted from the administration of any of the research procedures; and
- 'unexpected', i.e., an event that is not listed in the protocol as an expected occurrence

Reports of related and unexpected SAEs should be submitted within 15 days of the Chief Investigator becoming aware of the event, using the NRES SAE form for non-IMP studies. The Chief Investigator must also notify the Sponsor of all related and unexpected SAEs.

Local investigators should report any SAEs as required by their Local Research Ethics Committee, Sponsor and/or Research & Development Office.

Contact details for reporting SAEs

[contact]

Chief investigator: [name] ([contact], Vascular Lab/ D4, Hammersmith Hospital, [name]

Study Coordinator: [name] ([contact], Vascular Lab./D4, Hammersmith Hospital, [name])

6. ASSESSMENT AND FOLLOW-UP

There won't be a follow up. This study does not require any continued involvement of the participants after their scan. No information of the AutoDVT scan will be given to 2nd parties such as the GP or the clinical care team.

This study will only focus on acquired images of AutoDVT software. No incidental findings will be reviewed and reported. Participants will receive a DVT diagnostic scan by specialist, who can review and report potential findings.

The AutoDVT scan will not be available after the research has finished.
The collection of data will be finished by the 04.08.2022. The submission of the dissertation will be on the 26.08.2022.

7. STATISTICS AND DATA ANALYSIS

Personal data will be kept on the hospital computer systems. Anonymised data will be entered on a secure database by study Coordinator. The database itself will be a secure, validated system with restricted access, stored on a secure NHS server.

Data and all appropriate documentation will be stored for a minimum of 10 years after the completion of the study, including the follow-up period.

8. REGULATORY ISSUES

8.1. ETHICS APPROVAL

The Study Coordination Centre has obtained approval from the Research Ethics Committee (REC) of Imperial College and Health Research Authority (HRA). The study must also receive confirmation of capacity and capability from each participating NHS Trust before accepting participants into the study or any research activity is carried out. The study will be conducted in accordance with the recommendations for physicians involved in research on human subjects adopted by the 18th World Medical Assembly, Helsinki 1964 and later revisions.

8.2. CONSENT

(If study does not involve consent, this section is not relevant)

Consent to enter the study must be sought from each participant only after a full explanation has been given, an information leaflet will be offered, and time allowed for consideration. Signed participant consent should be obtained. The right of the participant to refuse to participate without giving reasons must be respected. All participants are free to withdraw at any time from the protocol treatment without giving reasons and without prejudicing further treatment.

8.3. CONFIDENTIALITY

Pseudonymised data is data that can be linked back to a person (e.g., coded data). It is considered both personal and identifiable data. Anonymised data is data that has no code and cannot be linked back to a person (e.g., aggregated data for publication, data without a code that cannot be linked back to a person).

The chief investigator will preserve the confidentiality of participants taking part in the study and is registered under the Data Protection Act.

Data will be pseudonymised.

No identifiable data will be transferred. Anonymised images will be shared with ThinkSono to further optimise AutoDVT software.

8.4. INDEMNITY

Imperial College London holds negligent harm and non-negligent harm insurance policies which apply to this study

8.5. SPONSOR

Imperial College London will act as the main Sponsor for this study. Delegated responsibilities will be assigned to the NHS trusts taking part in this study.

8.6. FUNDING There are no funding this study.

No payments are involved in this study, neither to participants, nor to principal investigator.

8.7. AUDITS

The study may be subject to audit by Imperial College London and their remit as sponsor and other regulatory bodies to ensure adherence to GCP and the UK Policy Framework for Health and Social Care Research.

9. STUDY MANAGEMENT

The day-to-day management of the study will be co-ordinated through the study coordinator, [name].

[figure not shown]
10. PUBLICATION POLICY

The research will be available to audit by regulatory authorities such as statistics at Imperial College, IRAS and supervisor at vascular Lab and the chief investigator [name] at Hammersmith Hospital. Publication may take place in medical peer reviewed journals.

APPENDICES

- CE Certificate AutoDVT software
- Patient information sheet 1
- Patient information sheet 2
- Consent form
- Reference list
- Summary of investigations, treatment and assesment

